26.0 Multi-Site Research*

Not Applicable

27.0 Protected Health Information Recording

1.0 Indicate which subject identifiers will be recorded for this research.

- Name
- Complete Address
- Telephone or Fax Number
- Social Security Number (do not check if only used for ClinCard)
- Dates (treatment dates, birth date, date of death)
- Email address , IP address or url
- Medical Record Number or other account number
- Health Plan Beneficiary Identification Number
- Full face photographic images and/or any comparable images (x-rays)
- Account Numbers
- Certificate/License Numbers
- Vehicle Identifiers and Serial Numbers (e.g. VINs, License Plate Numbers)
- Device Identifiers and Serial Numbers
- Biometric identifiers, including finger and voice prints
- Other number, characteristic or code that could be used to identify an individual
- None (Complete De-identification Certification Form)

2.0 Check the appropriate category and attach the required form* on the Local Site Documents, #3. Other Documents, page of the application. (Choose one.)

- Patient Authorization will be obtained. (Include the appropriate HIPAA language (see Section 14 of consent template) in the consent form OR attach the [HRP-900, HIPAA AUTHORIZATION](#) form.)

PROTOCOL TITLE: Virtual Reality-based Rehabilitation for Children with Traumatic Brain Injuries

- Protocol meets the criteria for waiver of authorization. (Attach the [HRP-901, WAIVER OF HIPAA AUTHORIZATION REQUEST](#) form.)
- Protocol is using de-identified information. (Attach the [HRP-902, DE-IDENTIFICATION CERTIFICATION](#) form.) (Checked "None" in 1.0 above)
- Protocol involves research on decedents. (Attach the [HRP-903, RESEARCH ON DECEDENTS REQUEST](#) form.)
- Protocol is using a limited data set and data use agreement. (Contact the Office of Technology Commercialization to initiate a Limited Data Use Agreement.

***Find the HIPAA forms in the [IRB Website Library, Templates](#).**

Attach the appropriate HIPAA form on the “Local Site Documents, #3. Other Documents”, page of the application.

3.0 How long will identifying information on each participant be maintained?

For duration of the study (two years) plus five additional years for publication, revision, and potential external inquiries/requests for re-analyzing data as part of the reproducible research effort.

4.0 Describe any plans to code identifiable information collected about each participant.

Eligible subject information will be entered on a hospital approved password protected computer password protected data registry in a locked research office. Enrolled subjects will be assigned a study ID number which will be how all study documents are labeled. The PI and limited trained research staff will be responsible for maintaining all components of the research record containing participants' identifying information.

5.0 Check each box that describes steps that will be taken to safeguard the confidentiality of information collected for this research:

ALL

Research records will be stored in a locked cabinet in a secure location
Research records will be stored in a password-protected computer file
The list linking the assigned code number to the individual subject will be maintained separately from the other research data
Only certified research personnel will be given access to identifiable subject information

6.0 Describe the provisions included in the protocol to protect the privacy interests of subjects, where "privacy interests" refer to the interest of individuals in being left alone, limiting access to them, and limiting access to their information. (This is not the same provision to maintain the confidentiality of data.)

PROTOCOL TITLE: Virtual Reality-based Rehabilitation for Children with Traumatic Brain Injuries

1. Research staff will be trained in the importance of protecting participants' privacy.
2. Each participant will be identified by a unique ID number rather than by name or medical record number. Participants' names will not appear on materials used during data analysis. The master list of participants' names and corresponding numbers will be kept only in electronic format in a password protected file in a secure folder on password protected computers.
3. All electronic data files will be stored in secure folder on a password-protected computer in a locked research office. Only members of the research team will have access to the files.
4. All hard copies of the data will be kept in a locked file cabinet in a locked office. No hard copies will be kept of the master list of participants' names and corresponding numbers. Only study staff will have access to these documents.
5. Publications of reports will not identify participants in the study or contain information leading to the identification of participants.

We have no plans to contact subjects after their study participation or to share their PHI with other investigators.

Confidential Health Information

1.0 Please mark all categories that reflect the nature of health information to be accessed and used as part of this research.

- Demographics (age, gender, educational level)
- Diagnosis
- Laboratory reports
- Radiology reports
- Discharge summaries
- Procedures/Treatments received
- Dates related to course of treatment (admission, surgery, discharge)
- Billing information
- Names of drugs and/or devices used as part of treatment
- Location of treatment
- Name of treatment provider
- Surgical reports
- Other information related to course of treatment
- None

2.0 Please discuss why it is necessary to access and review the health information noted in your response above.

Diagnosis will be used to identify patients. Age, gender, race, injury severity scores, including Glasgow Coma Scale score and Rancho Scale level, time spent in therapy, and neuropsychological testing results will be obtained from patient's

PROTOCOL TITLE: Virtual Reality-based Rehabilitation for Children with Traumatic Brain Injuries

individual medical records as control variables in the statistical analyses of this study so that potential confounding factors can be accounted for. Location of treatment (floor/room) is needed to locate the patient for participant recruitment purposes.

A Microsoft Excel spreadsheet will be created for use by the study recruiters in order to keep track of patients that fit the inclusion criteria and are recruited, and also of patients who meet exclusion criteria and are not recruited. The spreadsheet will include the following variables: first and last initial, age, gender, date screened, approached (Y/N), recruited (Y/N), and reasons for exclusion. If the patient is recruited, the spreadsheet will also include: MRN, patient name, guardian name(s), telephone number(s), email address(es), study ID number, study group (intervention or control), dates of VR therapy, and times of VR therapy. The rationale behind the eligibility spreadsheet is to track how many pediatric TBI patients are treated, and of those, how many are willing to participate in our study. This spreadsheet will be helpful for research project planning in order to guide our enrollment number prediction and also to reach out to families after discharge in order to schedule their follow-up research appointments (within 6 months). This password protected spreadsheet will be kept in a secure file folder on password protected computers in the Research Institute at Nationwide Children's Hospital. Only researchers on the IRB will have access to the secure folder where the file is located.

- 3.0 **Is the health information to be accessed and reviewed the minimal necessary to achieve the goals of this research?** Yes No
- 4.0 **Will it be necessary to record information of a sensitive nature?**
 Yes No
- 5.0 **Do you plan to obtain a federally-issued Certificate of Confidentiality as a means of protecting the confidentiality of the information collected?**
 Yes No

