6.0 Procedures Involved*

The procedure involved for the study is described in detail below:

1) Baseline assessment. All approximately 30 children will complete the NIH Toolbox Cognition Battery tests, CPT 3, Virtual Reality Assessment, and the TBI-QOL Short Form prior to the randomization sequence. Both the assessor and the child will be unaware of group assignment at this point. Additionally, data regarding baseline measurement including proportion of planned baseline measures that are completed and the duration of each assessment will be documented.

2) Intervention. Following the baseline assessment, the approximately 30 children will be randomly assigned to one of the following two groups: intervention group (VICT training) or control group (a comparable VR game without cognitive training). The random allocation sequence will be generated using a SAS-based randomization program with 1:1 allocation ratio and random block sizes of 2 and 4. Both groups will first be provided a tutorial to be familiar with the VR environment. The length of time for either intervention game will be a minimum of 15 minutes of total play. If they are in the hospital, they will play approximately 15 minutes per day during their stay. If they have already been discharged from the hospital, the length of time is a minimum of 15 minutes of total play but can be more spread across their choice of days. Trained researchers who generate the randomization sequence and implement the VR will not participate in any subsequent outcome assessment. Note that although the length of training will vary across children depending on their length of stay or if they have been discharged, this arrangement has unique advantages over a fixed length of training in that: a) it provides consistency with standard therapies children are scheduled to receive, ensuring intervention to meet children's medical needs; and b) it ensures consistent timing and sufficient retention rates for future assessment.

Additionally, AEs and SAEs will be monitored in real-time throughout the intervention. Quantitative user feedback such as sickness, fatigue, and time estimates will be measured at the end of both the first and the last VR session. The

PROTOCOL TITLE: Virtual Reality-based Rehabilitation for Children with Traumatic Brain Injuries

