17.0 Data Management* and Confidentiality

17.1 Describe the data analysis plan, including any statistical procedures or power analysis.

To examine the research paradigm (Aim 1), we will compute average number of children screened and enrolled per month, proportion of eligible children who enroll, treatment-specific retention rates, proportion of children who adhere to assigned condition, proportion of planned measures that are completed, and average duration of completing each measurement. To examine the feasibility and safety of the VICT program (Aim 2), the total number of AEs/SAEs, mean simulator sickness scores, and mean Borg exertion scores will be computed and compared between the intervention and control group using independent samples t-tests. Additionally, open-end feedback from children, parents, and clinicians on optimizing the VR games and best practices in protocol implementation will be synthesized and submitted to the VR development team for improvement. Finally, to explore the preliminary efficacy of the VICT program (Aim 2), difference scores from baseline to post-intervention and baseline to follow-up of the composite NIH Toolbox score, TBI-QOL, and Conners CPT 3 will be compared between the intervention group and the control group using analysis of covariance (ANCOVA) controlling for baseline scores. BRIEF2, CBCL-APS, and PedsQL (parent/child) scores at follow-up will be compared between the two groups using ANCOVA controlling for baseline scores. Cohen's d for core EFs changes will be computed as the preliminary intervention effect size. Finally, dosage effect will be evaluated within regression analyses, with dosage (0 for controls, cumulative hours of VICT training for intervention group) as the primary predictor and post-intervention NIH Toolbox scores as the outcome variable.

17.2 Describe the steps that will be taken to secure the data (e.g., training, authorization of access, password protection, encryption, physical controls, certificates of confidentiality, and separation of identifiers and data) during storage, use, and transmission.

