All data will be independently entered into a computerized database by trained research staff and verified by the PI. All data files will be maintained in the central electronic database system, REDCap (Research Electronic Data Capture), which is securely stored at the Research Institute at NCH. Each participant will be assigned a unique Study ID number. The master file that links the participants' names to their Study IDs will be maintained only in a password

protected file in a password-protected computer at the Research Institute at Nationwide Children's Hospital. All measurement and randomization procedures will only use Study IDs to record data without participants' names attached.

17.3 Describe any procedures that will be used for quality control of collected data.

Once data are collected and entered into electronic databases by one researcher, another researcher or the PI will independently verify the records to ensure accuracy.

17.4 Describe how data or specimens will be handle study-wide:

- *What information will be included in that data or associated with the specimens?*

The data to be collected include: Age, gender, race, injury severity scores, including Glasgow Coma Scale score and Rancho Scale level, gaming performance in the virtual program, and standard neuropsychological testing results. Demographic and medical variables listed above will be collected via patients' medical records. We will also include the amount of time spent in each rehab therapy using the Rehabilitation Provision of Services flow sheet in EPIC. Performance in games will be automatically recorded by the virtual reality computer program. Cognitive variables will be collected via standard neuropsychological tests.

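### Covariates must be named model by model: three follow-up ANCOVAs need baseline scores that are not scheduled, the dosage regression has no covariate, and section 27.0's control variables belong to no model

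*Combined protocol and SAP*

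**What the plan says.** Section 17.1 is the analysis plan. For the NIH Toolbox composite, TBI-QOL and Conners CPT 3, changes from baseline to post-intervention and to follow-up "will be compared between the intervention group and the control group using analysis of covariance (ANCOVA) controlling for baseline scores". For the remaining questionnaires, "BRIEF2, CBCL-APS, and PedsQL (parent/child) scores at follow-up will be compared between the two groups using ANCOVA controlling for baseline scores". An effect size is also planned, Cohen's d with no covariates named: "for core EFs changes will be computed as the preliminary intervention effect size". The dosage regression takes hours of VICT training (zero for controls) "as the primary predictor and post-intervention NIH Toolbox scores as the outcome variable". It names no other predictor, not even the baseline score.

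Section 27.0, under Confidential Health Information item 2.0, explains why records are accessed. It lists "Age, gender, race, injury severity scores, including Glasgow Coma Scale score and Rancho Scale level, time spent in therapy, and neuropsychological testing results", to be used "as control variables in the statistical analyses of this study so that potential confounding factors can be accounted for". No model and no time point is given. Section 17.4 says of therapy time: "We will also include the amount of time spent in each rehab therapy using the Rehabilitation Provision of Services flow sheet in EPIC". It gives no window either.

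Section 6.0 item 1 lists the baseline measures: the NIH Toolbox battery, CPT 3, the VR assessment and TBI-QOL. BRIEF2, CBCL-APS and both PedsQL forms appear only in item 4, the follow-up visit, and section 13.5 pays parents for Visit 3 only. On training, section 6.0 states: "If they are in the hospital, they will play approximately 15 minutes per day during their stay". Discharged children may spread their play over days of their choice. Section 9.1 sets no upper limit on training and lets preference and length of stay decide it.

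**The concern.** Section 17.1 does not say what role, if any, the variables in section 27.0 play. If they are not used, the stated reason for accessing them falls away. If they are used, section 17.1 is incomplete. Two gaps bear directly on results.

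1. Three of the planned ANCOVAs depend on a covariate that the schedule does not collect.
2. The dosage slope is not a purely randomised contrast. Controls sit at zero, but among VICT children the hours depend on stay and preference. If longer stays go with worse injury (an assumption), hours become a marker of severity, and the slope mixes training with prognosis.

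A third, lesser matter is timing. Therapy time and neuropsychological results are undated, and section 17.4 uses the latter term for the study's own cognitive tests. One undated list cannot serve both the arm comparisons and the dosage model.

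At stake are the estimates that a later trial would be planned on. If the covariates are settled after the data are seen, they can be chosen for their result.

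**Working it through.** The documents give no power, alpha, SD or effect size for efficacy, so there is no stated figure to reproduce. N is approximately 30 (section 12.1), allocated 1:1 (section 6.0). N=24 (20% loss) and all other inputs below are assumptions.

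**Step 1: can each stated model be fitted?**

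| Outcome | Covariate in 17.1 | At baseline in 6.0? |
|---|---|---|
| NIH Toolbox, TBI-QOL, CPT 3 | baseline score | yes |
| BRIEF2, CBCL-APS, PedsQL | baseline score | no, follow-up only |
| Dosage regression (NIH Toolbox) | none named | baseline score available, not used |

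The second row cannot be fitted from the scheduled data.

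**Step 2: dosage regression.** Simulation with N=30, no true effect, controls at 0 hours, log-normal hours, and 4,000 trials per row. Severity lowers the baseline score (coefficient -0.5) and lowers the outcome further at a given baseline score (-0.3). Entries are the share of trials with p<0.05.

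| Correlation of severity with log hours | No covariate | Baseline score | Baseline score + severity |
|---|---|---|---|
| 0 | 6% | 5% | 5% |
| 0.3 | 7% | 5% | 5% |
| 0.5 | 12% | 7% | 5% |
| 0.7 | 20% | 10% | 5% |

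The last column assumes severity is measured without error. GCS is a proxy, so real control would be less complete.

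**Step 3: cost of GCS in the arm comparisons.** With baseline score in the model, adding k covariates that explain a share R² of the residual variance multiplies the expected SE by sqrt((1-R²)(N-4)/(N-4-k)).

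- k=1, N=30, R²=0: sqrt(26/25) = 1.020. Break-even is R² = 1/26 = 3.8%.
- k=1, N=30, R² = 10%, 20%, 30%: 0.967, 0.912, 0.853.
- k=1, N=24, R²=0: sqrt(20/19) = 1.026. Break-even is 1/20 = 5%.
- Without a baseline score, k=1, N=30, R²=0: sqrt(27/26) = 1.019. Break-even is 1/27 = 3.7%.

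**Step 4: why not the whole section 27.0 list.** Age 1, gender 1, race 2 (three levels assumed), GCS 1, Rancho 1 and therapy time 1 make 7 df, leaving neuropsychological results uncounted. Residual df fall from 27 to 20 at N=30 and from 21 to 14 at N=24. If the additions are uninformative, the SE rises by sqrt(26/19) = 1.170 and sqrt(20/13) = 1.240.

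**Step 5: price of having no baseline for the three questionnaires.** With an assumed baseline-outcome correlation of 0.6 and N=30, adjustment would multiply the SE by sqrt((1-0.36)×27/26) = 0.815. Going without it therefore makes the SE 1/0.815 = 1.23 times as large. The randomised comparison stays unbiased; only precision is lost.

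**The case against.** **Section 27.0 is not the analysis plan.** It answers a privacy-form question about record access, and section 17.1 is explicit about its ANCOVAs. A reader might infer that the documents hold two rival plans, each equally binding. They do not: an analyst following the plan section fits the baseline-only model. Calling dosage the primary predictor also leaves room for others, and section 27.0's talk of confounding suits that regression. This largely stands, and it makes the mismatch an alignment matter. It does not rescue the three ANCOVAs that lack a baseline, and it does not say which covariates the dosage model should have.

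**Therapy time in the arm comparison.** A reader might infer that adjusting for it would bias the treatment effect. For inpatients it may accrue partly after randomisation, but it distorts the comparison only if assignment changes it, and the documents give no sign of that. The shift is zero if the arms do not differ. It is 0.05 to 0.20 SD only if they differ by 0.25 to 0.5 SD and each SD of therapy carries 0.2 to 0.4 SD of outcome, all assumed. Keeping it out is a precaution.

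**Movement between covariate sets.** A reader might take such movement as bias. In simulation (baseline-only SE about 0.30 SD), going from baseline-only to seven covariates moved the estimate by more than one SE in 9% to 17% of trials, and adding GCS alone did so in 0.3% to 9%. The mean shift was zero. This is chance movement. It is a reason to fix the model in advance and does not show that either model is wrong.

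**GCS is a judgement.** No document gives its association with outcome at a given baseline score, and below about 4% of residual variance it loses precision. Age is fixed just as early. This stands. The case for GCS is that eligibility requires it (section 10.2), it is already collected (section 17.4), and it measures injury severity.

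**Therapy time in the dosage model.** Leaving it out biases a null slope by 0.03 to 0.20 SD per SD of hours if hours and therapy correlate 0.5 to 0.8. That is below one sampling SD of the slope (0.13 to 0.22) in every case checked. With an unadjusted severity confounder also present, adding therapy time can make matters worse, for example from -0.029 to -0.070. It therefore belongs in a sensitivity analysis.

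**Conclusion.** The point holds in limited form. The baseline-adjusted ANCOVAs for BRIEF2, CBCL-APS and PedsQL cannot be fitted from the scheduled data; this rests on the text alone. The dosage regression as written is open to confounding. Its size depends on assumptions: false-positive rates of 12% to 20% at correlations of 0.5 to 0.7 between severity and log hours, and close to nominal if hours are unrelated to severity. Section 27.0 needs aligning with section 17.1.

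The documents do not support saying that the planned arm comparisons are biased. The unadjusted Cohen's d is not touched by this point.

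Severity is modest. Section 2.2 states no hypotheses, section 4.1 makes efficacy the second endpoint, and the feasibility and safety endpoints are unaffected. The change is still worth making because it is cheap.

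**What to change.** In section 17.1:

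- **NIH Toolbox composite, TBI-QOL, CPT 3:** arm + baseline score + GCS (continuous, 1 df) as the governing model, with the baseline-only ANCOVA as a labelled sensitivity analysis.
- **BRIEF2, CBCL-APS, PedsQL at follow-up:** arm + GCS, unless the sponsor chooses to collect these before randomisation. In that case add the baseline score.
- **Dosage regression:** add baseline NIH Toolbox score and GCS. Add concurrent therapy time, with a stated window, as a sensitivity analysis. Describe the result as observational.

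In section 27.0, state which listed variable enters which model. Keep therapy time and neuropsychological results obtained after randomisation out of the arm comparisons.

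Cost: wording only, since GCS and therapy time are already to be collected. GCS takes 1 df in each arm comparison, about 2% in SE at N=30 (2.6% at N=24 where a baseline score is in the model) if it is uninformative. The dosage model loses 2 df, from 28 to 26 at N=30. Collecting the three questionnaires before randomisation would add child and parent time at the first visit, for which section 13.5 has no parent payment.
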